4.3.1 Dermatological irAEs

Rule out non-inflammatory causes. If a non-inflammatory cause is identified, treat accordingly and continue therapy per protocol (Table 3).

Confidential Page 37 of 78

Table 3: Dermatological irAE Management Algorithm

	Dermatological irAEs	
CTCAE Grade of Rash	Management	Follow-Up
Grade 1-2 Covering ≤30% body surface area	 Symptomatic therapy (e.g., antihistamines, topical corticosteroids). Continue AGEN1884 therapy per protocol. 	 If persists >1 to 2 weeks or recurs: Consider skin biopsy. Delay AGEN1884 therapy. Consider 0.5-1 mg/kg/day methylprednisolone IV or oral equivalent. Once improving, taper corticosteroids over ≥1 month; consider prophylactic antibiotics for opportunistic infections; and resume AGEN1884 therapy per protocol. If worsens: Treat as grade 3-4.
Grade 3-4 Covering >30% body surface area; life-threatening consequences	 Delay or discontinue AGEN1884 therapy per protocol. Consider skin biopsy. Dermatology consult 1-2 mg/kg/day methylprednisolone IV or IV equivalent. 	 If improves to grade 1: Taper corticosteroids over ≥1 month; add prophylactic antibiotics for opportunistic infections. Resume AGEN1884 therapy per protocol.

CTCAE: Common Terminology Criteria for Adverse Events; irAE: immune-related adverse event; IV: intravenous; kg: kilogram; mg: milligram

Confidential Page 38 of 78

4.3.2 Gastrointestinal irAEs

Rule out non-inflammatory causes. If non-inflammatory cause is identified, treat accordingly and continue therapy. Opiates/narcotics may mask symptoms of perforation. Infliximab should not be used in cases of perforation or sepsis (Table 4).

Table 4: Gastrointestinal irAEs Management Algorithm

Gastrointestinal irAEs							
CTCAE Grade of Diarrhea/Colitis	Management	Follow-Up					
Grade 1 Diarrhea: <4 stools/day over baseline. Colitis: asymptomatic.	 Continue AGEN1884 therapy per protocol. Symptomatic treatment. 	 Close monitoring for worsening symptoms. Educate subject to report worsening immediately. Consider symptomatic treatment including hydration, electrolyte replacement, dietary changes (e.g., American Dietetic Association colitis diet), and loperamide. If worsens: Treat as grade 2 or 3-4. 					
Grade 2 Diarrhea: 4-6 stools per day over baseline; IV fluids indicated <24 h; not interfering with activities of daily living (ADL). Colitis: abdominal pain; blood in stool.	 Delay AGEN1884 therapy per protocol. Symptomatic treatment. 	 If improves to grade 1: Resume AGEN1884 therapy per protocol. If persists >5 to 7 days or recurs: 0.5-1 mg/kg/day methylprednisolone or equivalent. When symptoms improve to grade 1, taper corticosteroids over ≥1 month; consider prophylactic antibiotics for opportunistic infections; resume AGEN1884 therapy per protocol. If worsens or persists >3 to 5 days with oral corticosteroids: Treat as grade 3-4. 					
Grade 3-4 Diarrhea (grade 3): ≥7 stools per day over baseline; incontinence; IV fluids ≥24 h; interfering with ADL. Colitis (grade 3): severe abdominal pain, medical intervention indicated, peritoneal signs. Grade 4: life-threatening, perforation	 Discontinue AGEN1884 therapy per protocol. 1-2 mg/kg/day methylprednisolone IV or equivalent. Add prophylactic antibiotics for opportunistic infections. Consider lower endoscopy. 	 If improves: Continue corticosteroids until grade 1, then taper over ≥1 month. If persists >3 to 5 days, or recurs after improvement: Add infliximab 5 mg/kg (if no contraindication). Note: Infliximab should not be used in cases of perforation or sepsis. 					

ADL: activities of daily living; CTCAE: Common Terminology Criteria for Adverse Events; h: hour; irAE: immune-related adverse event; IV: intravenous; kg: kilogram; mg: milligram.

Confidential Page 39 of 78

4.3.3 Pulmonary irAEs

Rule out non-inflammatory causes. If non-inflammatory cause is identified, treat accordingly and continue therapy per protocol. Evaluate with imaging and pulmonary consultation (Table 5).

Table 5: Pulmonary ir AE Management Algorithm

Pulmonary irAEs											
CTCAE Grade of Pneumonitis	Management	Follow-Up									
Grade 1 Radiographic changes only.	 Consider delay of AGEN1884 therapy per protocol. Monitor for symptoms every 2-3 days. Consider pulmonary and infectious disease consults. 	 Re-image every ≥3 weeks. If worsens: Treat as grade 2 or grade 3-4. 									
Grade 2 Mild to moderate new symptoms	 Delay AGEN1884 therapy per protocol. Pulmonary and infectious disease consults. Monitor symptoms daily; consider hospitalization. 1 mg/kg/day methylprednisolone IV or oral equivalent. Consider bronchoscopy, lung biopsy. 	 Re-image every 1-3 days. If improves: When symptoms return to near baseline, taper corticosteroids over ≥1 month, then resume AGEN1884 therapy per protocol, and consider prophylactic antibiotics. If not improving after 2 weeks or worsening: Treat as grade 3-4. 									
Grade 3-4 Severe new symptoms; new/ worsening hypoxia; life- threatening.	 Discontinue AGEN1884 therapy per protocol. Hospitalize. Pulmonary and infectious disease consults. 2-4 mg/kg/day methylprednisolone IV or IV equivalent. Add prophylactic antibiotics for opportunistic infections. Consider bronchoscopy, lung biopsy. 	 If improves to baseline: Taper corticosteroids over ≥6 weeks. If not improving after 48 hours or worsening: Add additional immunosuppression (e.g., infliximab, cyclophosphamide, IV immunoglobulin, mycophenolate mofetil). 									

CTCAE: Common Terminology Criteria for Adverse Events; irAE: immune-related adverse event; IV: intravenous; kg: kilogram; mg: milligram

Confidential Page 40 of 78

4.3.4 Hepatic irAEs

Rule out non-inflammatory causes (e.g., alcohol use, acute viral hepatitis, flare up from chronic hepatitis, co-infection [e.g., with hepatitis D], etc.). If a non-inflammatory cause is identified, treat accordingly and continue therapy per protocol. Consider imaging for obstruction and a hepatologist consult (Table 6).

Table 6: Hepatic ir AE Management Algorithm

	Hepatic irAEs										
CTCAE Grade of Liver Test Elevation	Management	Follow-Up									
Grade 1 AST or ALT >ULN to 3 x ULN and/or total bilirubin >ULN to 1.5 x ULN.	Continue AGEN1884 therapy per protocol.	 Continue liver function tests (LFT) monitoring per protocol. If worsens: Treat as grade 2 or grade 3-4. 									
Grade 2 AST or ALT >3 to ≤5 x ULN and/or total bilirubin >1.5 to ≤3 x ULN. If subject has concurrent AST or ALT >3 x ULN and total bilirubin >2 x ULN, discontinue AGEN1884 therapy per protocol (Hy's Law)	 Delay AGEN1884 therapy per protocol. Increase frequency of monitoring to every 3 days. 	If returns to baseline: Resume routine monitoring; resume AGEN1884 therapy per protocol. If elevations persist >5 to 7 days or worsen: 0.5-1 mg/kg/day methylprednisolone IV or oral equivalent. When LFT returns to grade 1 or baseline, taper corticosteroids over ≥1 month, consider prophylactic antibiotics for opportunistic infections, and resume AGEN1884 therapy per protocol.									
Grade 3-4 AST or ALT >5 x ULN and/or total bilirubin >3 x ULN.	 Permanently discontinue AGEN1884 therapy per protocol. Increase frequency of monitoring to every 1-2 days. 1-2 mg/kg/day methylprednisolone IV or oral equivalent.* Add prophylactic antibiotics for opportunistic infections. Consult gastroenterology. Consider obtaining MRI/CT scan of liver and liver biopsy if clinically warranted. 	 If returns to grade 2: Taper corticosteroids around 4 to 6 weeks. If does not improve in >3 to 5 days, worsens, or rebounds: Add mycophenolate mofetil 1 g twice daily. If no response within an additional 3-5 days, consider other immunosuppressants per local guidelines. 									

Confidential Page 41 of 78

	Hepatic irAEs	
CTCAE Grade of Liver Test Elevation	Management	Follow-Up
For subjects in Phase 2 with HCC and elevated baseline LFT Dose delay for the following: Baseline AST, ALT < 2 x ULN with an increase to ≥ 5 x ULN Baseline AST, ALT ≥ 2 x ULN with an increase to >3 x the baseline level Elevations of AST, ALT ≥ 500 IU/L or 20 x ULN regardless of baseline level Baseline total bilirubin ≤ 1.5 x ULN and increase to ≥ 2 x ULN Baseline total bilirubin >1.5 x ULN and increase to ≥ 2 x baseline level Elevations of total bilirubin ≥ 3 x ULN regardless of baseline level	Dose delay or discontinue AGEN1884 therapy. 1-2 mg/kg/day methylprednisolone IV or oral equivalent.* Consider hepatologist consult Increase frequency of monitoring to every 3 days	 If returns to grade <1 or baseline level within 1 week then taper corticosteroids over ≥ 1 month If symptoms and laboratory resolve to grade ≤1 or baseline levels and steroids have been tapered to a prednisone level ≤ 10mg/day or equivalent for at least a week, may consider resuming AGEN1884 If does not improve in >3 to 5 days, worsens, or rebounds: Add mycophenolate mofetil 1 g twice daily. If no response within an additional 3-5 days, consider other immunosuppressants per local guidelines and hepatologist consult. Also, permanently discontinue. If symptoms and laboratory do not resolve to grade ≤1 or baseline levels within 3 weeks or steroids cannot be tapered to a prednisone level ≤ 10 mg/day or equivalent within 9 weeks, AGEN1884 must be permanently discontinued. All cases considered for re-treatment should be discussed with the medical monitor

^{*} The recommended starting dose for grade 4 hepatitis is 2 mg/kg/day methylprednisolone IV.

ALT: alanine aminotransferase; AST: aspartate aminotransferase; CT: computed tomography; CTCAE: Common Terminology Criteria for Adverse Events; HCC: hepatocellular carcinoma; irAE: immune-related adverse event; IV: intravenous; kg: kilogram; LFT: liver function test; mg: milligram; MRI: magnetic resonance imaging; ULN: upper limit of institutional normal.

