4.1.2 Dosing Delay Criteria

Prior to every AGEN1884 administration, laboratory values will be reviewed. AGEN1884 administration will be delayed for the following adverse events (AEs), if the following AEs occur on the day of planned AGEN1884 dosing:

- Either febrile neutropenia or neutropenia <500 cells/mm³ for >1 week despite the use of growth factors.
- Any grade ≥2, non-skin, drug-related AE except for fatigue and laboratory abnormalities
- Any grade 3 drug-related laboratory abnormality (except lymphopenia, AST, ALT, total bilirubin, or asymptomatic lipase or amylase).
 - o Grade 3 lymphopenia does not require a dose delay.
 - o If the subject has a baseline AST, ALT, or total bilirubin that is within normal limits, dosing should be delayed for drug-related grade ≥2 toxicity.
 - o If the subject has a baseline AST, ALT, or total bilirubin within the grade 1 toxicity range, dosing should be delayed for drug-related grade ≥3 toxicity.
 - o Any grade 3 drug-related amylase or lipase abnormality that is not associated with symptoms or clinical manifestations of pancreatitis does not require dose delay.
- Any grade 3, skin, drug-related AE.
- Any AE, laboratory abnormality, or intercurrent illness that, in the judgment of the investigator, warrants delaying the dose of study medication.
- For subjects in Phase 2 with HCC and an elevated baseline liver function test:

Dose delay for the following:

- Baseline AST, ALT \leq 2 x ULN with an increase to \geq 5 x ULN
- Baseline AST, ALT ≥ 2 x ULN with an increase to ≥ 3 x the baseline level
- Elevations of AST, ALT ≥500 IU/L or 20 x ULN regardless of baseline level
- Baseline total bilirubin ≤ 1.5 x ULN and increase to ≥ 2 x ULN
- Baseline total bilirubin >1.5 x ULN and increase to \geq 2 x baseline level
- Elevations of total bilirubin $\ge 3x$ ULN regardless of baseline level

Permanently discontinue for

- Elevations of ALT ≥20 x ULN regardless of baseline level
- Clinical Hepatic Decompensation regardless of lab values as follows:
 - New onset clinical ascites
 - Upper gastrointestinal bleeding due to portal hypertension
 - o Encephalopathy
 - Coagulopathy due to liver disease
 - Worsening Child-Pugh score to 9

Confidential Page 34 of 78

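### For drug-related liver test elevations handled as immune-related, Protocol 4.1.2, Table 6 and 4.4.2 give different dosing actions and no order of precedence

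*Protocol*

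**What the plan says.** Protocol 4.1.2 (Dosing Delay Criteria) has two general bullets that could catch a raised liver test on a dosing day. The first covers "Any grade ≥2, non-skin, drug-related AE except for fatigue and laboratory abnormalities", so laboratory values fall outside it. The second covers "Any grade 3 drug-related laboratory abnormality (except lymphopenia, AST, ALT, total bilirubin, or asymptomatic lipase or amylase" abnormalities, so the liver tests fall outside that one too. Two baseline-dependent sub-bullets then deal with them. For a subject with a "baseline AST, ALT, or total bilirubin that is within normal limits, dosing should be delayed for drug-related grade ≥2 toxicity". For a subject with a "baseline AST, ALT, or total bilirubin within the grade 1 toxicity range, dosing should be delayed for drug-related grade ≥3 toxicity". A further bullet lets the investigator delay for any laboratory abnormality by judgment.

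Protocol 4.3.4, Table 6 (Hepatic irAE Management Algorithm) sets its actions by on-study grade. Outside the HCC row it attaches no baseline condition to them. The grade 2 row, "Grade 2 AST or ALT >3 to ≤5 x ULN and/or total bilirubin >1.5 to ≤3 x ULN", carries a delay. The grade 3-4 row (AST or ALT above 5 x ULN, or bilirubin above 3 x ULN) carries "Permanently discontinue AGEN1884 therapy per protocol".

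Protocol 4.4.2 (Permanent Treatment Discontinuation) requires a permanent stop for grade 3 and grade 4 adverse drug reactions, with listed exceptions. Its grade 3 exception for isolated laboratory values does not extend to liver function tests. Grade 2 reactions follow a separate rule. Treatment may go on if the event is back to grade 1 or below by the end of the current cycle. Otherwise the next cycle's infusion is withheld, and treatment stops for good if the event has still not resolved by the end of that cycle.

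**The concern.** A site with one laboratory result in hand can reach different dosing decisions depending on which section it opens. The subjects most exposed are those who enter with mildly raised liver tests, whom the eligibility criteria allow. The first consequence is for safety: the action at a given grade is not settled by the text.

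The second is for reporting. Safety and tolerability are a primary endpoint, and SAP 8.6.2 counts any elevated liver function test as an adverse event of special interest. The same SAP section tabulates treatment-emergent events leading to permanent discontinuation and, within immune-mediated clusters, the percentages leading to dose hold and to drug discontinuation. If sites follow different sections, identical laboratory courses can enter those tables differently.

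**Working it through.** No sample size, power or event figure is involved. The check sets the passages side by side.

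**1. Who is in scope.** Outside HCC, inclusion criterion 9 (Protocol 3.2.1) admits AST and ALT up to 2.5 x ULN and bilirubin up to 1.5 x ULN. Table 6 defines "Grade 1 AST or ALT >ULN to 3 x ULN and/or total bilirubin >ULN to 1.5 x ULN". Since 2.5 is below 3 and the bilirubin limits are equal, every eligible non-HCC subject with a value above ULN starts in the grade 1 range. Phase 2 HCC subjects with elevated baseline tests are set aside because 4.1.2 and Table 6 each give them their own rules.

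**2. Which events are in scope.** Section 4.1.2 covers drug-related values on the planned dosing day. Table 6 covers hepatic irAEs after non-inflammatory causes are ruled out. The two meet where a drug-related elevation is handled as immune-related, and the comparison is limited to that overlap.

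**3. Actions by baseline and grade.**

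| Baseline | On-study grade | Section 4.1.2 | Table 6 | Section 4.4.2 |
|---|---|---|---|---|
| Normal | 2 | Delay | Delay | Depends on resolution by end of cycle |
| Grade 1 | 2 | No required delay; investigator judgment | Delay | Depends on resolution by end of cycle |
| Normal | 3-4 | Delay | Permanent discontinuation | Permanent discontinuation, listed exceptions apart |
| Grade 1 | 3-4 | Delay | Permanent discontinuation | Permanent discontinuation, listed exceptions apart |

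**4. Illustration.** Take a non-HCC subject with baseline ALT 2 x ULN.
- At 4 x ULN on a dosing day (grade 2), 4.1.2 does not require a hold and Table 6 does. If the elevation has persisted past the end of the previous cycle, 4.4.2 also withholds the infusion.
- At 6 x ULN (grade 3-4), 4.1.2 says delay, while Table 6 and 4.4.2 say stop permanently. The same holds had the baseline been normal.

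**5. A sharper case inside the grade 2 row.** Table 6 calls for discontinuation when AST or ALT exceeds 3 x ULN together with bilirubin above 2 x ULN. With ALT above 3 and up to 5 x ULN and bilirubin above 2 and up to 3 x ULN, each value is grade 2. If both baselines were grade 1, 4.1.2 does not require even a delay.

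**6. Search for a tie-breaker.** None is stated.
- The laboratory footnote to Table 10 (Schedule of Assessments) sends the pre-dose decision to 4.1.2 alone.
- The end of 4.1.2 points to Table 6 only for Phase 2 HCC subjects diagnosed with autoimmune hepatitis, and sets no precedence.
- Table 6 qualifies its actions as being per protocol without naming a section.
- A note in 5.8.6.4 adds a further wording: grade 3 or 4 events may be considered for discontinuation.

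**The case against.** The strongest reply concerns grade 3-4. Section 4.1.2 is a list of delay criteria and, outside its HCC bullet, contains no discontinuation rule. An instruction not to dose today does not exclude a separate instruction to stop for good. Section 4.4.2, the section on permanent discontinuation, points the same way as Table 6. This is a fair reading and weakens that half of the point. What remains is that the protocol never says so, and Table 10 leads sites only to the section that mentions delay.

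At grade 2 there are two replies. First, 4.1.2 allows delay by judgment; that permits a hold but does not require one, whereas Table 6 does. Second, the per-protocol qualifier in Table 6 might be taken to import the 4.1.2 thresholds. No section is named, however, and on that reading the grade 2 delay row would have no force for a subject with a grade 1 baseline, which Table 6 does not say.

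It is also fair that Table 6 is introduced as an aid to investigators, and that the effect on SAP tables is limited. The hepatitis cluster in SAP 8.6.2 does not list raised ALT or AST among its terms, so elevations coded that way would not enter that cluster's dose-hold percentage. The discontinuation tables are descriptive.

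A reader might infer that the hepatic stop rule is contradictory at every grade for every subject with a grade 1 baseline, or that the grade 3-4 mismatch is peculiar to such subjects. The documents support neither. HCC subjects with raised baseline tests have separate rules, Table 6 reaches only elevations handled as immune-related, 4.4.2 agrees with Table 6 in direction at grade 3-4, and the grade 3-4 difference in wording applies equally to a normal baseline.

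**Conclusion.** The inconsistency is real but narrower than a general contradiction in the hepatic stopping rules. The firm part is a grade 1 baseline with an on-study grade 2 value, where three sections give three different rules. The weaker part is grade 3-4 with a normal or grade 1 baseline: 4.1.2 says delay while Table 6 and 4.4.2 say permanent stop. A pre-dose-hold reading would resolve this if the protocol stated it.

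The conclusion assumes that the elevation is drug-related, that it is handled as immune-related, and that the subject is outside the HCC elevated-baseline rules. The documents do not give the number of subjects affected. Phase 1 is complete and Protocol 3.1 plans about 40 non-HCC subjects in Phase 2, with some allowance for additional enrolment. That planned figure limits the continuing reach of the grade 2 conflict but does not estimate it, because only those with a grade 1 baseline and a later qualifying elevation are concerned. The point is an internal inconsistency that should be corrected. It takes no position on which action is right.

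**What to change.** Reconcile Protocol 4.1.2, Table 6 and 4.4.2 together. Correcting only the first two would leave the separate grade 2 rule in 4.4.2 in place. For each baseline category (normal, grade 1, and the HCC elevated-baseline group) and each on-study grade, state one action in all three places. Add a sentence giving the order of precedence between the delay criteria, the irAE algorithm and the permanent discontinuation list. Extend the laboratory footnote in Table 10 so that it refers to all the governing sections, and align the note in 5.8.6.4. The clinical lead must decide the action for each cell.

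The cost is wording in a protocol amendment. No change to sample size, endpoints or SAP methods follows from it.

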4.3.5 Endocrine irAEs

Rule out non-inflammatory causes. If non-inflammatory cause is identified, treat accordingly and continue therapy per protocol. Consider visual field testing, endocrinology consultation, and imaging (Table 7).

Confidential Page 42 of 78

Table 7: Endocrine ir AE Management Algorithm

	Endocrine irAEs										
Endocrine Disorder	Management	Follow-Up									
Asymptomatic TSH abnormality	 Continue AGEN1884 therapy per protocol. If TSH <0.5 x lower limit of normal (LLN) or TSH >2 x ULN, or consistently out of range in 2 subsequent measurements: Include free thyroxine (T4) at subsequent cycles as clinically indicated; consider endocrinology consult. 										
Symptomatic endocrinopathy	 Evaluate endocrine function. Consider pituitary scan. Symptomatic with abnormal lab/pituitary scan: Delay AGEN1884 therapy per protocol; 1-2 mg/kg/day methylprednisolone IV or oral equivalent; initiate appropriate hormone therapy. No abnormal lab/pituitary MRI scan but symptoms persist: Repeat labs in 1-3 weeks, MRI in 1 month. 	 If improves (with or without hormone replacement): Taper corticosteroids over ≥1 month and consider prophylactic antibiotics for opportunistic infections. Resume AGEN1884 therapy per protocol. Subjects with adrenal insufficiency may need to continue corticosteroids with mineralocorticoid component. 									
Suspicion of adrenal crisis (e.g., severe dehydration, hypotension, shock out of proportion to current illness)	 Delay or discontinue AGEN1884 therapy per protocol. Rule out sepsis. Stress dose of IV corticosteroids with mineralocorticoid activity. IV fluids. Consult endocrinologist. If adrenal crisis ruled out, treat as above for symptomatic endocrinopathy. 										

irAE: immune-related adverse event; IV: intravenous; kg: kilogram; LLN: lower limit of normal; mg: milligram; MRI: magnetic resonance imaging; TSH: thyroid stimulating hormone; ULN: upper limit of normal.

Confidential Page 43 of 78

4.3.6 Renal irAEs

Rule out non-inflammatory causes. If non-inflammatory cause is identified, treat accordingly and continue therapy per protocol (Table 8).

Table 8: Renal ir AE Management Algorithm

	Renal irAEs										
CTCAE Grade of Creatinine Elevation	Management	Follow-Up									
Grade 1 Creatinine >ULN and >baseline but ≤1.5 x baseline	 Continue AGEN1884 therapy per protocol. Monitor creatinine weekly. 	 If returns to baseline: Resume routine creatinine monitoring per protocol. If worsens: Treat as grade 2 or grade 3-4. 									
Grade 2-3 Creatinine >1.5 x baseline to ≤6 x ULN	 Delay AGEN1884 therapy per protocol. Monitor creatinine every 2-3 days. 0.5-1.0 mg/kg/day methylprednisolone IV or oral equivalent. Consider renal biopsy 	 If returns to grade 1: Taper corticosteroids over ≥1 month, consider prophylactic antibiotics for opportunistic infections, and resume AGEN1884 therapy and routine creatinine monitoring per protocol. If elevations persist > 7 days or worsen: Treat as grade 4. 									
Grade 4 Creatinine >6 x ULN	 Discontinue AGEN1884 therapy per protocol. Monitor creatinine daily. 1.0-2.0 mg/kg/day methylprednisolone IV or IV equivalent. Consult nephrologist. Consider renal biopsy. 	If returns to grade 1: Taper corticosteroids over ≥1 month and add prophylactic antibiotics for opportunistic infections.									

CTCAE: Common Terminology Criteria for Adverse Events; irAE: immune-related adverse event; IV: intravenous; kg: kilogram; mg: milligram; ULN: upper limit of normal.

Confidential Page 44 of 78

